Study Design: To address Aims 2 and 3, we will use a randomized controlled trial. A total of 300 adults with arthritis, aged 18 and older, will be recruited throughout the community. Participants will be randomized to either Walk with Ease (WWE-T) or Wait list control. The WWE-T program will be 6 weeks in duration, like the AAEBI version of WWE, and will include two phone calls each week: one group call and one individual call. Assessments will be conducted before randomization, immediately after the 6-week program, and at 6 months and 1 year. There will be no intervention-specific contact with participants following the 6-week program. Primary outcomes are pain and physical function. Secondary outcomes are weight, objectively measured physical activity, depressive symptoms, self-efficacy, weight, blood pressure, work loss, and health care utilization.

Procedures:

Recruitment: Participants will be recruited using effective recruitment strategies used in the past as well as with the assistance of DHEC, the SC Department of Aging, and Lupus Foundation of America. All recruitment procedures are provided in more detail in section D.2.

Screening: Participants will be screened by telephone or online to ensure they meet study criteria. Interested and eligible participants will be scheduled for a baseline appointment and mailed an informed consent form and study materials to review prior to their baseline visit.

Informed Consent: At the baseline appointment, study staff will review the consent form with participants and answer any questions participants may have regarding their participation. To ensure the consent form is understandable to the study population, the consent form will be written using short sentences and non-technical terms, with a reading level at or below an eighth-grade level. Interested participants will sign the approved informed consent document and will be given a copy for their records.

Randomization: After completing the baseline assessment, participants will be randomized in a 1:1 ratio to either: (1) WWE-T or (2) Wait list control. Randomization, stratified by age (<65 years and ≥65 years) and sex, will be done using randomly permuted blocks. The study team member conducting the randomization phone call will open the sealed envelope and reveal randomization to the participant. The study team member will describe the condition, provide the appropriate program materials via mail, and review study expectations.

Randomized Conditions:

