- 1.) **Walk with Ease by Telephone Program.** Our Walk with Ease by Telephone (WWE-T) program is adapted from the original 6-week community-based group walking program developed by the Arthritis Foundation for adults with arthritis. After randomization, all participants in WWE-T will be given an Arthritis Foundation Walk with Ease Guidebook and a brief overview of the program. The program uses motivational strategies, which includes action planning, goal setting, and social support. Additionally, WWE provides participants with appropriate health education necessary to safely increase walking and exercise into their daily lives and assists in tailoring the program to fit individuals' unique needs and goals. Examples of topics include exercise and arthritis, preparing to walk (e.g., identifying appropriate footwear, location, and walking pace), stretching, and overcoming barriers including pain and discomfort. Participants will work towards walking at least 30 minutes/day for 3 days/week, as this goal is consistent with the evidence-based WWE program.

Phone Sessions for WWE-T. Participants in WWE-T will receive 2 phone calls each week for 6 weeks. Each week, one phone call will be one-on-one with a WWE certified trained leader and the second call will be a group call led by the WWE leader and will include other WWE-T participants. During group phone sessions, the WWE-T leader will cover topics described above relating to exercise and arthritis. Group calls will include 12-16 participants, as recommended by previous studies. Group calls will last approximately 45 - 60 minutes in duration. During

University of South Carolina Protocol v4

individual phone sessions, the WWE leader will focus on tailoring the WWE-T program for the individual and setting weekly walking goals. The WWE leader will also ensure that safety issues are assessed and addressed. Individual calls will be approximately 10 – 15 minutes in duration. WWE leaders will document attendance, topics discussed, any participant symptoms/adverse events, and call durations.

- 2.) **Wait List Control.** Participants randomized to Wait List Control will receive the WWE-T program following the completion of the 1-year assessment. Besides scheduling for and sending reminders for each assessment, there will not be contact with participants in the Wait List Control.

Measures:

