Data Analysis: After data collection and cleaning, baseline characteristics of the groups will be compared. Variables which differ between the groups at baseline will be used as covariates in the outcome models. For each of the Aim 2 primary and secondary outcomes, a generalized linear model will estimate group means at baseline, six weeks, six months and one year. Each model will include factors for group (2 levels), time (4 levels), group-by-time interactions and the required covariates. In the event of participants being lost to follow-up or otherwise missing data from the 6-week, 6-month and/or 1-year times, the models will provide estimates using Full Information Maximum Likelihood with robust standard errors, interpretable under an Intent to Treat principle.

For each outcome at each follow-up time, a statistically significant (at the 0.05 level) group by time interaction in the hypothesized direction will be interpreted as supporting the research hypothesis. The magnitude of each intervention effect will be computed by a pre-defined contrast of baseline to follow-up change in the group minus baseline to follow-up change in the Wait List Control, adjusted for covariates. All four time points for each outcome will be examined with a single model to best account for the full covariance structure over time. All analyses will be completed using SAS (SAS Institute Inc, Cary, NC).

We will evaluate the recruitment and retention strategies used during the proposed study, focusing on successful strategies used to increase participation of adults with arthritis, particularly among those with low socioeconomic status. During the recruitment and screening of participants, participants will be asked to report how they heard of the program. We will also examine recruitment numbers over time in relation to recruitment activities. Following the completion of the program, we will categorize recruitment avenues (e.g., saw flyer, word of mouth) and sites (e.g., local rheumatologist site, lupus support group) and calculate the percentage of those screened, not interested, ineligible, and enrolled. Percentages will be calculated among the total sample recruited as well as specifically for those of low

University of South Carolina Protocol v4

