socioeconomic status (i.e., income <150% of poverty guidelines) and other demographic (e.g., race) or clinical variables (e.g., pain). We will compare enrollment yields by avenues and sites, using total sample and those with low socioeconomic status, using chi-square tests or Fisher's exact test if cell frequencies are less than 5. Identifying the highest yielding recruitment sources, especially for those with low socioeconomic status, will help to inform recruitment strategies used in future programs. Retention of participants in WWE-T will be examined at program completion (6 weeks) and each follow-up assessment (6 months and 1 year). Overall retention rates and percentages of specific reasons for attrition (e.g., loss to follow-up, no longer interested, medical issues) will be calculated among the total sample and by those with low socioeconomic status (i.e., income <150% of poverty guidelines), and other demographic (e.g., race) or clinical variables (e.g., baseline pain). We will also examine retention and specific reasons for attrition based on recruitment avenue and site. Independent samples t tests and chi-square tests (or Fisher's exact test for those with cells less than 5) will be used to examine differential attrition.

Data Management: All surveys will be administered via paper or online via REDCap (secure, web application for building and managing online surveys and database – managed by Health Sciences South Carolina). Any paper documents will be stored in a locked filing cabinet at the TecHealth Center at University of South Carolina. All computer files will be password protected. Only the study team will have access to the data.

D. PROTECTION OF HUMAN SUBJECTS

1.TARGET POPULATION

Inclusion Criteria: The target population will include adults ≥ 18 years old who meet criteria for the CDC's definition of self-reported arthritis.^{54,55} Specifically, participants who respond yes to the following question will be eligible: "Have you ever been told by a doctor or other health professional that you have some form of arthritis, rheumatoid arthritis, gout, lupus, or fibromyalgia?" Additionally, participants must be able to read and write in English, plan to live in the Columbia, SC region for the next year, complete all baseline measures, and be willing to be randomized to either study condition.

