Exclusion Criteria: Participants will only be excluded if they have any contraindications to exercise (besides arthritis) per the Physical Activity Readiness Questionnaires,⁵⁶ are pregnant, breastfeeding, or planning to become pregnant in the next year, have a serious cognitive impairment, or are currently or have previously participated in a WWE program within the last 12 months.

Sample Size: In order to assure sufficient statistical power to detect clinically meaningful effects, we relied on information from a previous study by Wilcox, et. al.¹¹ for an estimate of variability in the VAS Pain scale and physical function tests including the 30-second chair stands and six-minute test. The Steps to Health study evaluated two 12-week self-directed multicomponent exercise programs for adults with arthritis.¹¹ Clinically meaningful magnitude of changes were suggested by Bennell et al.⁵⁷ as 11 points for VAS pain, 1.3 repetitions for the chair stand test and 20-50 meters for the six-minute walk. Estimated power is based on a simplified analysis (t-tests) without covariate adjustments. A statistical significance level of 0.05 was used.

A sample of 120 participants per group would provide 80% or greater power to detect a clinically meaningful difference in each primary outcome, with a minimum effect size of $d=.37$, assuming that the variability within our sample is comparable to that observed in the earlier study from a similar population (see Table 2). We anticipate that some participants may be lost to follow-up before the conclusion of the study. Therefore, we propose inflating the required sample size by 25% to account for potential attrition and recruiting 300 participants total, with 150 to be randomized into each treatment condition.

2.RECRUITMENT PLANS:

Participants will be recruited using effective recruitment strategies used in the past as well as with the assistance of DHEC, the SC Department of Aging, and Lupus Foundation of America across Richland,

University of South Carolina Protocol v4

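### Housemates can be enrolled and randomized to opposite arms, so a wait-list participant may have the program at home and the contrast may be biased toward no difference

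*Combined protocol and SAP*

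**What the plan says.** Section D.1 (Target Population) closes the exclusion list with the word *only*: "Participants will only be excluded if they have any contraindications to exercise (besides arthritis" and so on. The remaining reasons are pregnancy-related, serious cognitive impairment, and the person's own exposure to the program, for those who "are currently or have previously participated in a WWE program within the last 12 months". That last reason does not reach a housemate. The inclusion criteria end with the requirement to "complete all baseline measures, and be willing to be randomized to either study condition" and set no household condition. Elsewhere, household appears only in the income definition of low socioeconomic status (Section D.2).

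Under Randomization in Section C, "participants will be randomized in a 1:1 ratio to either" arm, and the scheme is described in full as "Randomization, stratified by age (<65 years and ≥65 years) and sex, will be done using randomly permuted blocks". No rule covers people who live together.

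Under Randomized Conditions, "all participants in WWE-T will be given an Arthritis Foundation Walk with Ease Guidebook", and program materials go out by mail. The wait-list arm is to have no contact beyond assessment scheduling and reminders, and receives WWE-T only after the 1-year assessment.

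**The concern.** The plan treats exposure to Walk with Ease as something that spoils the comparison. It excludes people who recently took part, and it keeps the wait-list arm away from the program for a year. Neither safeguard covers a wait-list participant whose spouse, parent or sibling is in WWE-T. That person could read the Guidebook and walk with someone who is being coached in goal setting and social support. The Background section itself reports benefit from the self-directed format, so some transfer without leader calls is plausible.

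Any such transfer improves the control arm and shrinks the difference in pain and function. It could do so at each follow-up. As written, it could not be examined afterwards, because the plan records neither household links nor control exposure to program materials. The sample size allows for attrition but not for contamination.

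**Working it through.** **Inputs from Section D.1, Sample Size:** 120 per group, d = 0.37, significance level 0.05, power of at least 80%, and simple t-tests. Sidedness is not stated; I assume two-sided.

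**The plan's own figure.** A two-sample t-test with noncentrality 0.37 × √(120/2) = 2.87 on 238 degrees of freedom has power 81.4%. The stated power reproduces. The smallest d with 80% power at this size is 0.363, so the margin is used up once average dilution exceeds 1 − 0.363/0.37, about 1.9%.

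**Chance of a split.** An opposite-sex couple falls in two different strata, so the partners are allocated independently and have about a one-half chance of opposite arms. Two housemates in the same stratum and the same permuted block are slightly more likely than that to be split. I use one-half.

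**Dilution.** Let h be the share of participants with an enrolled housemate (in pairs), g the share of controls living with a WWE-T participant, and e the fraction of the program effect such a control gains.

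- g = h/2
- diluted d = 0.37 × (1 − g × e)

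The documents give neither h nor e; both are assumptions. With e = 0.5:

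| Controls exposed (g) | Participants with an enrolled housemate (h = 2g) | Pairs among 300 (300 × h/2) | Diluted d | Power, 120 per group | 11-point pain difference becomes |
|---|---|---|---|---|---|
| 0 | 0 | 0 | 0.370 | 81.4% | 11.0 |
| 3% | 6% | 9 | 0.364 | 80.3% | 10.8 |
| 5% | 10% | 15 | 0.361 | 79.5% | 10.7 |
| 10% | 20% | 30 | 0.352 | 77.4% | 10.5 |

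Example, second-last row: 0.37 × (1 − 0.05 × 0.5) = 0.361, and 11 × (1 − 0.025) = 10.7.

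**Sensitivity to e, at 5% of controls exposed:** e = 0.1 gives 81.1%, e = 0.25 gives 80.5%, e = 0.5 gives 79.5%, and e = 1 gives 77.4%.

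**With one participant per household:** g = 0, so d stays at 0.37 and power at 81.4%, with no change in sample size.

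**The case against.** The strongest reply is that the effect is probably small. Recruitment covers three counties and uses newspaper and radio advertisements, emails, flyers and social media. Nothing in the documents suggests that many couples will join. Having 10% of controls exposed would take about 30 co-enrolled pairs. A housemate also gets much less than a participant, who has six individual and six group calls, so a half-sized gain may be generous. The power baseline is itself a simplified t-test at the smallest effect size, and slipping just under 80% there does not mean the planned four-timepoint model fails. All of this stands, and it limits the point to a possible and probably modest bias.

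The recruitment evidence should not be pressed either. Word of mouth appears in the Data Analysis section, where "we will categorize recruitment avenues (e.g., saw flyer, word of mouth" is an example of how sources will be classified. The recruitment plan does not list it. Group dining programs and support groups are listed, and couples or relatives could come through them, but no count follows.

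A reader might also infer that correlated outcomes within a home undermine the planned standard errors, since the model has no household term. The design does not support that. Under independent allocation, a same-arm pair adds to the variance of the contrast and a split pair subtracts from it by the same amount, so on average they cancel. Inflation appears when housemates are put in the same arm: the factor is about 1 + h × ICC, for example 1 + 0.40 × 0.30 = 1.12 with assumed values of 40% of participants in pairs and ICC 0.30.

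**Conclusion.** The gap is real. The closed exclusion list, individual randomization and the absence of any household rule together allow housemates to be split between arms, and nothing else in the documents prevents it. If a wait-list housemate takes up the material or the walking, the bias is toward no difference.

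It would go too far to say that the contrast *is* diluted. The documents give no co-enrolment rate and no uptake rate, and they do not say where calls are taken or how long a control housemate would have the content. With half the effect passed on, a two-sided test and a one-half chance of a split, the loss is about 1 power point at 3% of controls exposed, 2 points at 5% and 4 points at 10%. The case for acting rests on the thin margin above 80% and the low cost of prevention, not on a demonstrated loss.

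**What to change.** Ask at screening whether anyone in the household is already in the study, and add to the exclusion criteria: *another member of the household is already enrolled in this study*. This removes within-home contamination with no change in sample size. The cost is one question and a few volunteers declined.

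For any housemates already enrolled, record the household link and prespecify a sensitivity analysis of the primary outcomes that leaves out shared households.

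I would not assign a later housemate to the first member's arm. That person's allocation would be known before consent and baseline, which defeats the concealment the sealed envelopes provide and empties the requirement of willingness to be randomized to either condition. It would also bring in the variance inflation described above.

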8. COMPENSATION

Participants will receive \$25 for completing the baseline and 6-week assessments, \$40 for completing the 6-month assessment, and \$50 for completing the 1-year assessment. Payment options will be in the form of a physical gift card or an e-gift card from Amazon, a retail store or grocery store.

9. WITHDRAWAL:

Participants will be informed they can leave the research at any time without penalty. If a participant decides to withdraw, no more information will be collected. The participants will be made aware of this during the consent process.

Any data collected during their participation may be used by the investigators for the purposes described above. Choosing not to be in the study will not result in any penalty or loss of benefit to which participants are entitled. Specifically, the choice not to be in this study will not negatively affect a participant's right to any present or future medical treatment or his/her present or future employment.

E. REFERENCES/LITERATURE CITATIONS

4. Wyatt B. Impact of the Arthritis Foundation's Walk With Ease Program on Arthritis Symptoms in African Americans. *Prev Chronic Dis.* 2014;11. doi:10.5888/pcd11.140147
6. Centers for Disease Control and Prevention. *Lifestyle Management Programs for Arthritis.* Accessed January 18, 2021. <https://www.cdc.gov/arthritis/interventions/index.htm>
